Adherence to Medical Treatments for Telemedicine Patients (Protocol)

NCT04180475

Version Date: 04/09/2019

PROTOCOL**Background****1. Provide the scientific background, rationale and relevance of this project.**

Proper adherence to prescribed medications is a fundamental requirement for effective health outcomes. The possible consequences of poor medication adherence include reduced effectiveness of treatments, deterioration of health conditions, longer recovery time, increased cost, irrecoverable damages to health, hospitalization, and even death. Despite the severe consequences, the medication adherence rate among patients is significantly low^{1, 2, 3}. According to the World Health Organization (WHO), “Adherence to long- term therapy for chronic illnesses in developed countries averages 50%. In developing countries, the rates are even lower”¹. Poor medication adherence is a public health problem, and WHO identifies it as a worldwide problem of striking magnitude. It causes about 33-69% of all the medication associated hospital admissions in the U.S.⁴.

One of the main reasons for poor medication adherence is forgetfulness. People often forget to take medication at the appropriate time, and even sometimes take wrong dosages. Though forgetfulness is more prevalent in people with reduced cognitive ability such as the elderly, it is also very common to healthy and young people due to factors like daily routine, habits, and changes in medication regimen. Several studies show that medication adherence is improved significantly with the use of automated reminder systems^{5, 6, 7}.

A number of smart phone applications for medication reminder and tracking are available in app stores^{8,9}. Researchers have also designed, developed and evaluated reminder systems using smart phones^{10, 11}. However, smart phone apps are not convenient and effective enough for medication reminder and tracking. Though smart phones can be used by one hand when it is laid on or hung against some surfaces, most of the times users need to hold the phone by one hand and use it by another. Occupation of the hands for using the phones, and the attention required to use the apps justify that smartphone-based systems are significantly intrusive, and are not convenient, particularly for long-term and complex medication regimens. Also, a user is very likely to miss a reminder at home when the phone is far enough from his/her location at the time the reminder is given. For instance, a user may miss a reminder when he/she is busy in the kitchen, but the phone is in the bedroom far away from the user. Moreover, remainders may be missed while listening to songs, TVs or videos even if the phone is located near the user. In many situations like in meetings and classrooms, smart phones typically need to be kept silent, and users often forget to return the devices back to the non-silent mode when silence is not required any more. It is very likely that a user misses some reminders in such scenarios.

This study will test the feasibility of MedRem, a novel medication reminder and tracking system on wearable wrist devices, specifically with the Apple Watch 4. The study team will load the MedRem app onto two Apple Watch 4s for use during the study. As the device is

placed on the wrist, it is free from the above-mentioned limitations of smart phones. However, one of the major challenges in developing interactive systems for the wrist devices is their form factor. The touch screens available on these devices are tiny and much smaller compared to smart phones and tablet computers. MedRem enables user interactions by incorporating speech recognition and text-to-speech features along with clever interface design. The tiny display of the device is used for minimal inputs and outputs, while a user can retrieve and provide more information from/to the system through voice commands. Personalized models are built and updated over time to reduce errors in recognizing users' voice commands, and thus better user experience is provided.

Smart wearable devices like smart watches and wrist bands are usually enriched with many features like touch screens, microphones, sensors, Bluetooth and Wi-Fi. These devices are being used widely in healthcare applications including activity tracking, wellbeing monitoring, and reminders. Harmony is a hand wash monitoring and reminder system that uses inertial sensors of the smart watches in detecting hand wash activities of the wearer, and Bluetooth beacon-based localization technique to trigger reminders when required¹². A diary-like system for diabetes patients is presented in another study that uses both smartphones and smartwatches to log information from and provide reminders to diabetes patients¹³. SPARK is a framework that combines smartphones and smartwatches together in monitoring symptoms of patients with Parkinson's Disease. It also supports physicians in providing tele-interventions to the patients¹⁴. Fabian et al. propose to show pictures of the drugs on the display of the wrist device to reduce confusion of the patients when multiple drugs need to be taken¹⁵. Some smartphone apps also synchronize reminders with smart watches¹⁶. However, these systems use only the small display of the wrist device, and therefore cannot provide detailed information related to a reminder using the wrist device only. Also, wrist devices used in the existing systems do not support rescheduling the reminders. Most of these reminders and tracking systems are aimed for specific group of patients or users. In contrast, MedRem is a general-purpose medication reminder and tracking system that can be customized according to the patient's needs. It combines speech recognition and text- to-speech technologies with intelligent interface design in providing reminders and tracking intakes.

One of the more complex issues in healthcare surrounds patient non-compliance with medical advice and treatment recommendations. Coupled with challenges in access to care faced by patients in rural or other underserved areas, the development of innovative solutions to chronic disease management is imperative. The UVA Center for Telehealth has long provided services to patients regardless of geographic barriers, and, in particular, for those facing serious health disparities. As is the case with traditional in-person services, clinicians are challenged to ensure (or monitor) that daily adherence to treatment is completed. The field of remote patient monitoring is growing, and new sensing and actuation technologies have the potential to monitor for adherence and to support interventions that improve adherence. The UVA School of Engineering and Applied Sciences and the UVA Center for Telehealth will collaborate on this study.

The proliferation of inexpensive sensing and actuation technology has the potential to bring improved health care to underserved areas. Telemedicine has made great strides in this regard. However, one of the most challenging problems is supporting patients in adhering to the (daily) treatments. Excellent remote health care will not work if the patients do not act on the advice and treatments. New, inexpensive, and easy to use technology (such as proposed here) has the potential to track adherence and, importantly, provide just-in-time, adaptive and learned interventions to increase adherence and thereby improve the health in rural communities. In this work we will focus on stroke patients, but the results of this work can be generalized to other medical conditions which will increase the future funding possibilities. Such solutions will not only improve health, but also reduce hospital readmissions. Underlying technical solutions will also have impact in producing robust and usable wearables and be a novel for voice processing in certain important contexts.

In this study, we will deploy the MedRem system to obtain a small amount of clinical and social acceptance data for a particular type of stroke patient. We will have two phases of deployment. In the first phase, we will deploy the system to control/test subjects. In the second phase, we will deploy the system in homes (each for 4 weeks) in order to collect some preliminary pre-pilot data. These systems will be deployed to stroke patients. Since this is a small study we will focus on stroke victims who are able to participate with a voice command home health system (i.e. no prohibitive cognitive impairments or language deficits), who have requirements for home- based therapy regimens (i.e. physical/occupational therapy), and who require medications for secondary stroke prevention (e.g. antithrombotic therapy to prevent ischemic stroke, stroke risk factor management with blood pressure, diabetes, cholesterol medications). We will identify patients by working with [name], a neurologist in the UVA Health System, who has extensive experience collaborating on mobile telehealth projects in stroke patients.

We will focus on the clinical value of improved rehabilitation by voice-based reminder interventions. The smart watch will identify exercise and provide the frequency and type of intervention for both medications and exercise. For exercise, we will interact with the patients (via audio on the watch) at specific times of the day to determine if they have completed that exercise. These messages will be prerecorded and loaded onto the MedRem app. We will also measure heart rate and heart rhythm using the smart watch's heart monitoring capabilities and inertial measurement units using the smart watch's accelerometer, gyroscope, and magnetometer.

Then, in future proposals other issues will be investigated including ability with respect to activity of daily living skills, attitudes, depression, anxiety, long-term use, and effect of reminders related to side effects. We would also extend the work to address caregiver issues of their own health and stress and anxiety. It is also possible to extend the use of the smart watches to assess the quality of the exercise regimen.

Objectives/Hypothesis

The purpose of this study (Phase 1) is to:

Version Date: 04/09/19

Page Number: 4 of 10

- determine the feasibility of the Apple Watch medication/exercise reminder system by deploying the system to two control subjects.

The purpose of this study (Phase 2) is to:

- assess the subjects' adherence to medications, exercise and checking heart rate (and quality of the exercise), with the use of MedRem
- assess the acceptance and usability of the MedRem system.

The hypothesis is that patients will use the system and that there are improvements in rehabilitation time and capability compared to averages for this population.

Study Design: Biomedical

1. Will controls be used? Yes.

► **IF YES, explain the kind of controls to be used.**

We will test the system with two control patients.

2. What is the study design? Case series

3. Does the study involve a placebo? No.

Human Participants

Ages: ≥18 years

Sex: All

Race: All

Subjects- see below

1. Provide target # of subjects (at all sites) needed to complete protocol.

Phase 1: 2

Phase 2: 8

2. Describe expected rate of screen failure/ dropouts/withdrawals from all sites.

Phase 1: 0%

Phase 2: 20%

3. How many subjects will be enrolled at all sites?

Phase 1: 2

Phase 2: 10

4. How many subjects will sign a consent form under this UVa protocol?

12. Phase 1 subjects will sign a Dry Run consent.

Inclusion/Exclusion Criteria

1. List the criteria for inclusion

Version Date: 04/09/19

Page Number: 5 of 10

Phase 1 (Controls)

- 18 – 75 years old
- Good general health (self-reported), with no history of CVA
- English-speaking
- Willingness and ability to comply with scheduled visits and study procedures

Phase 2 (Stroke Patients)

- 18 – 75 years old
- English-speaking
- Willingness and ability to comply with scheduled visits and study procedures
- Have requirements for home- based therapy regimens (i.e. physical/occupational therapy)
- Require medications for secondary stroke prevention (e.g. antithrombotic therapy to prevent ischemic stroke, stroke risk factor management with blood pressure, diabetes, cholesterol medications).
- Have a Modified Rankin Scale for Neurologic Disability (MDS) of 2 – 4

2. List the criteria for exclusion

Phase 1 (Controls)

- Pregnant women, fetuses, neonates, children, prisoners, cognitively impaired, non-English speaking subjects
- Prohibitive cognitive impairments or language deficits
- Does not have wireless internet connection at home

Phase 2 (Stroke Patients)

- Pregnant women, fetuses, neonates, children, prisoners, cognitively impaired, non-English speaking subjects
- Have a Modified Rankin Scale for Neurologic Disability (MDS) of 0-1 or 5
- Prohibitive cognitive impairments or language deficits
- Significant weakness, dystonia, or spasticity that will prevent proper use and response to the Apple Watch device
- Live in nursing home or rehabilitation facility
- Does not have wireless internet connection at home

3. List any restrictions on use of other drugs or treatments. n/a

Statistical Considerations

1. Is stratification/randomization involved? No.

2. What are the statistical considerations for the protocol?

Phase 1:

The objective of Phase 1 is to determine the feasibility of the Apple Watch medication/exercise reminder system by deploying the system to two control subjects.

The primary endpoint of this phase to assess the usability of the system and to work out any technical problems. The usability will be assessed by the 'Test Patient MedRem Usability Survey.' (see attached)

Phase 2:

The objective of Phase 2 is to determine the effectiveness of the Apple Watch medication/exercise reminder system by deploying the system to stroke patients. The goal is to assess the clinical value of improved rehabilitation by voice-based reminder interventions.

The primary endpoint of this phase is to assess the patients' adherence to medications and exercise. Adherence will be measured by patient responses to questions prompted by the MedRem System.

The secondary endpoint of this phase is to assess the acceptance and usability of the system. Acceptance and usability will be measured by the Intervention Patient MedRem Usability Survey (see attached). Steps taken and distance covered data will also be collected from the Apple Watch.

3. Provide a justification for the sample size used in this protocol.

2 control subjects will suffice in determining the feasibility of the device software.

8 study subjects will suffice in determining the effectiveness of the device software. We will aim to recruit 10 subjects, accounting for a dropout rate of 20%.

4. What is your plan for primary variable analysis?

The primary variable will be analyzed by counting whether the patient responded to the MedRem system prompts and whether the patient confirms that the medication was taken or therapy exercise was completed.

5. What is your plan for secondary variable analysis?

The secondary variable will be measured based on the survey results. We will also analyze the steps taken, and distance covered data collected from the Apple Watch.

6. Have you been working with a statistician in designing this protocol? No.

7. Will data from multiple sites be combined during analysis? No.

Study Procedures-Biomedical Research

1. What will be done in this protocol?

Phase 1:

The MedRem system will be deployed to two control subjects who will interact with the system by responding to medication and exercise reminder prompts. Subjects will be provided with oral and written information regarding the watch and MedRem system. Test subjects will not take any sham medications or exercise regimens, but will be provided a sham reminder schedule. They will simply respond verbally to prompts and press a button on the watch when finished speaking as if they are taking the medication or doing the exercise. After one week of interacting with the system, the study team will follow up with the subject and determine the functionality of the system by asking survey questions. If changes need to be made, the subject will interact with the system for one more week to test out the new changes. At the end of each week of the testing period, the subject will respond to a survey over the phone (see attached 'Test Patient MedRem Usability Survey').

Phase 2:

After a patient is identified, recruited, and consented, the study team will introduce the MedRem system to the stroke patient. The patient will be thoroughly trained before taking the device home, and will be given written information and instructions for the AppleWatch and the MedRem system. A member of the study will have to come to the patient's home to connect the apple watch to the patient's home wifi. The subject will be asked to wear the watch while awake during their daily activities. Subjects will be given contact information for a member of the study team to be available by telephone if they have questions once they begin to use the watch. The subject's physician and physical therapist, who are also members of the study team, will collect all medications and treatment regimens for the subject and give that information to the programming team. The programming team will upload the medication and treatment regimens to the MedRem system. The licensed providers, on the study team, will review the list of medication and physical therapy exercises before the information is sent to the subject's MedRem system on their Apple Watch.

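### Phase 2 can describe use, self-confirmed adherence and usability, but cannot support its rehabilitation, clinical-value or effectiveness statements

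*Combined protocol and SAP*

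**What the plan says.** The Objectives/Hypothesis section lists two purposes for Phase 2. One is adherence to medication, exercise and heart-rate checking, with exercise quality in brackets. The other is acceptance and usability. It then states: "The hypothesis is that patients will use the system and that there are improvements in rehabilitation time and capability compared to averages for this population".

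Statistical Considerations item 2 goes further: "The objective of Phase 2 is to determine the effectiveness of the Apple Watch medication/exercise reminder system", followed by "The goal is to assess the clinical value of improved rehabilitation by voice-based reminder interventions". The Background carries nearly the same sentence: "We will focus on the clinical value of improved rehabilitation by voice-based reminder interventions". Item 3 gives the sample size: "8 study subjects will suffice in determining the effectiveness of the device software", and then "We will aim to recruit 10 subjects, accounting for a dropout rate of 20" per cent.

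On measurement, item 2 says: "Adherence will be measured by patient responses to questions prompted by the MedRem System". Item 4 analyses this by counting responses and confirmations. The secondary endpoint is a usability survey, with steps and distance also collected. Study Design item 2 calls the study a case series, Statistical Considerations item 1 says there is no randomization, and the Background describes 4-week home deployments made "in order to collect some preliminary pre-pilot data".

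**The concern.** The stated aims and the described data do not match. Four statements concern benefit: the rehabilitation clause of the hypothesis, the clinical-value goal (stated twice), the effectiveness objective, and the claim that 8 patients suffice for effectiveness. The endpoints concern something else, namely whether patients answer the app, what they tell it, and how usable they find it.

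What is at stake is the conclusion the study may draw. Under the present wording, a good response rate or favourable survey could be reported as meeting an effectiveness objective, although nothing collected shows what would have happened without the device.

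**Working it through.** **The plan's own figure.** Inputs from Statistical Considerations item 3: 8 patients needed, 20% dropout. 8/(1 − 0.20) = 10, which agrees with the stated 10. The 8 cannot be reproduced: no significance level, power, effect, standard deviation (SD) or precision target is given.

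**What each statement needs, against what the text supplies.**

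- *Rehabilitation clause.* It needs an outcome for time and for capability, a time point and a reference value. No Phase 2 endpoint measures either. The Modified Rankin Scale appears only in the eligibility criteria (2 to 4 included), with no repeat planned. Steps and distance come nearest, but have no pre-MedRem value, norm or stated link to rehabilitation. The reference is mentioned but has no value or source.
- *Clinical-value goal.* It needs the same missing outcome. The Background leaves ability in daily living to future proposals.
- *Effectiveness objective.* It needs a contrast with not having MedRem. The only controls are two Phase 1 testers in self-reported good health with no stroke history. They follow a sham schedule and carry out no real regimen, so they cannot serve as a comparator. Nor can an effect on adherence be estimated: that effect is adherence with MedRem minus adherence without it, and the second term is never observed because adherence is recorded only through MedRem's prompts.
- *Sufficiency of 8.* It needs an effect to detect or a precision to reach. Neither is stated.

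**Illustration on assumed inputs.** Suppose an outcome and a fixed, known average did exist, tested by a two-sided one-sample t-test at 0.05 (all assumed). With n = 8, power is 8%, 23% and 50% for true differences of 0.2, 0.5 and 0.8 SD, and reaches 80% only at about 1.16 SD. For pure description, the 95% half-width for a patient-level mean is t(0.975, n − 1)/√n SDs: 2.365/√8 = 0.84 SD at n = 8, and 2.262/√10 = 0.72 SD at n = 10. These figures show what 8 or 10 patients can carry. They do not measure an error in the plan, and the conclusion does not depend on them.

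**Two listed objectives without an endpoint.** Study Procedures schedules heart-rhythm checks twice a day and records a time stamp for each ECG. Over 4 weeks that is 2 × 28 = 56 scheduled checks per patient, yet Statistical Considerations has no endpoint for them. The objective also speaks of heart rate where the procedure speaks of heart rhythm. Exercise quality is an objective in Objectives/Hypothesis but only a possible extension in the Background; motion-sensor data are planned, but no quality measure is defined.

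**The case against.** The strongest reply is that the narrow scope is largely present already. The Background calls the data pre-pilot, the two listed purposes are adherence and acceptance/usability, the endpoints broadly follow them, and no test or efficacy threshold is planned. This stands, and it is why the remedy is mainly one of wording. It does not remove the four statements that say otherwise.

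A second reply is that effectiveness of the device software may be meant technically, since the preceding sentence speaks of the software's feasibility. That reading is open. But the sentence follows an objective about the system deployed to stroke patients and a goal about clinical value, so it needs rewording on either reading.

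Third, the survey attachments were not available, including the unnamed one-month survey in Study Procedures. A rehabilitation item in them cannot be excluded. No endpoint or analysis in the text uses one.

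A reader might also infer three stronger points that the documents do not support:

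- *That use will be overstated because only completers are analysed.* The plan names no analysis set, and its counting rule allows unanswered prompts to be counted. Human Participants item 2 gives the 20% for screen failure, dropout and withdrawal together, so it cannot all be read as stopping after receiving the watch.
- *That natural recovery would confound the result.* The hypothesis compares with population averages, which would themselves include recovery, and no time since stroke is set. The defect is the unspecified outcome and reference.
- *That the sponsor will claim efficacy.* The wording permits it; nothing in the documents shows an intention.

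**Conclusion.** The concern holds as a mismatch between aims and design, and should be fixed. As described, Phase 2 cannot support the rehabilitation clause, the clinical-value goal, the effectiveness objective or the statement that 8 patients suffice for effectiveness. It also cannot estimate improvement in adherence. Confidence in the mismatch is high, subject to the unseen attachments.

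No error size can be given, because the plan specifies no outcome, baseline or reference from which to compute one.

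It would be too strong to infer that Phase 2 is without value. The prompt counts, survey results and activity data remain sound as descriptions, and they answer whether patients use the system.

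**What to change.** 1. Objectives/Hypothesis: limit the hypothesis to use, acceptance and usability, and delete the rehabilitation clause.
2. Background focus sentence, and the Phase 2 objective and goal in Statistical Considerations item 2: replace with *to describe use of MedRem, self-confirmed adherence to medication and exercise prompts, and acceptance and usability*.
3. Statistical Considerations item 3: replace the Phase 2 text with *8 patients (10 recruited) for descriptive estimates; the sample is not sized to determine effectiveness*.
4. Statistical Considerations item 4: for every patient who receives the watch, including those who stop early, report the proportions of prompts responded to and confirmed, separately for medication and exercise. Show individual values and the time of stopping. Report use over the full 4-week schedule, with prompts after stopping counted as not used, separately from adherence up to stopping, because these are different quantities. No particular interval method is required.
5. Report scheduled heart checks completed, from the ECG time stamps, after reconciling heart rate in the objectives with heart rhythm in the procedures.
6. Reconcile exercise quality: define a measure from the planned sensor data, or move it to future work.
7. Report steps and distance descriptively, with no efficacy claim.

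The cost is wording edits in three sections and a short summary of logs and time stamps already planned. No new data, visits or patients are needed unless the sponsor chooses to define an exercise-quality measure. The downside is that the trial gives up any claim of effectiveness or rehabilitation benefit.

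### Phase 2 is said to determine effectiveness, but without an adherence comparator it can only describe adherence during MedRem use

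*Combined protocol and SAP*

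**What the plan says.** Statistical Considerations, item 2, on Phase 2: "The objective of Phase 2 is to determine the effectiveness of the Apple Watch medication/exercise reminder system". The next sentence adds: "The goal is to assess the clinical value of improved rehabilitation by voice-based reminder interventions". The Background has a near-identical statement about clinical value.

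Item 3 justifies the sample size in two sentences: "8 study subjects will suffice in determining the effectiveness of the device software" and "We will aim to recruit 10 subjects, accounting for a dropout rate of 20" percent.

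The primary endpoint is adherence to medication and exercise. Item 2 says how it is obtained: "Adherence will be measured by patient responses to questions prompted by the MedRem System". Under item 4 the analysis consists of "counting whether the patient responded to the MedRem system prompts" and whether the patient confirms the dose or exercise. Item 2 also notes: "Steps taken and distance covered data will also be collected from the Apple Watch".

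Study Design names a case series, and Statistical Considerations, item 1, rules out randomization.

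Other sections are more modest. The Background calls the four-week home data preliminary and pre-pilot. Under Objectives/Hypothesis, the Phase 2 purpose is to assess "adherence to medications, exercise and checking heart rate (and quality of the exercise), with the use of MedRem", along with acceptance and usability. The hypothesis there has two parts: that patients will use the system, and that rehabilitation time and capability will improve relative to population averages.

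**The concern.** Effectiveness is a causal claim: adherence with MedRem against adherence without it. Such a claim needs some value for the second term, and the plan appears to supply none.

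Adherence recorded during use combines several things: what these patients would have done anyway, any effect of MedRem, the weekly contact with the study team (Study Procedures, Phase 2), and the selection of patients willing and able to comply (inclusion criteria). Nothing collected separates them.

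What is at stake is the conclusion. With the objective and the sample-size justification worded as they are, a descriptive percentage from about eight patients could be reported as proof that the system works.

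**Working it through.** **1. The plan's own figure.** Enrolment = completers / (1 − dropout) = 8 / (1 − 0.20) = 8 / 0.8 = 10. This reproduces. The 8 itself cannot be recomputed, because the documents give no significance level, power, effect size, reference rate, standard deviation or target precision.

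**2. Search for a comparator for adherence.**

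- *Phase 1 controls.* Two people in good general health with no stroke history, given a sham reminder schedule and no real regimen. They have no adherence to compare.
- *Pre-MedRem measurement.* The Phase 2 procedures go from consent and training straight to use of the watch. The endpoint consists of answers to MedRem prompts, so it does not exist before MedRem starts.
- *The 50% in the Background.* A general figure for chronic illness in developed countries. No analysis uses it.
- *The population averages in the hypothesis.* These concern rehabilitation time and capability, not adherence. No value, source, endpoint or analysis is attached to them.
- *Device data.* ECG time stamps, steps and distance do not depend on the patient's verbal answers, but they are described only during watch use and with no comparator.
- *Usability surveys.* The attachments are not in the text available. The protocol describes them as usability surveys given at the end of each week and after one month of use; no baseline adherence question is mentioned.

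**3. What the missing term does.** Implied effect = adherence during use − usual adherence. Assume 80% during use (the documents give no value).

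| Usual adherence | Implied effect |
|---|---|
| 50% (Background figure) | 80 − 50 = +30 points |
| 80% (assumed) | 80 − 80 = 0 points |

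Sample size does not enter this calculation, so the range is the same for 8, 10 or 1,000 patients. Other assumed values would give other ranges.

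**4. What 8 patients do provide.** The 95% t-interval half-width for mean adherence is t(0.975, 7) × SD / √8 = 0.836 × SD. For assumed SDs of 10, 20 and 30 points this is 8.4, 16.7 and 25.1 points. This is precision for a description and has no bearing on attribution.

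**5. If a baseline or reference value were added.** With n = 8, a two-sided 5% paired or one-sample t-test has 80% power at a standardized change of about 1.16. At an assumed SD of 20 points (1.156 × 20) that is about 23 points.

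**The case against.** The best reply has three parts.

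First, item 3 speaks of the effectiveness of the device *software*, directly after saying that two controls suffice for the *feasibility* of that software. Read alone, it could mean technical performance: whether the software prompts patients and captures their answers. A count can inform that without a comparator. This ambiguity is real and softens the criticism of item 3. It does not rescue item 2, which names the reminder system and follows at once with the clinical value of improved rehabilitation.

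Second, the protocol limits itself elsewhere: a small study, pre-pilot data, a case series, adherence during use. No test, success threshold or go/no-go rule depends on effectiveness. That is correct, and it caps the seriousness of the point: a few sentences are out of line with the rest. It is also the reason to bring them into line.

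Third, the 30-point range comes from an assumed 80% and a background figure. That is also correct. It shows how the gap works and measures nothing about this trial.

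A reader might go further and infer that Phase 2 needs a control group, or that 8 patients are too few. The documents do not support either inference. For the descriptive aim given in the Background and Objectives no comparator is needed, and no precision target is stated against which 8 could be judged too small. Nor is the whole hypothesis beyond reach: item 4's response count addresses whether patients use the system.

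**Conclusion.** The point holds as a mismatch between stated aim and design, and should be fixed. Item 2 promises an effectiveness conclusion that the described design cannot give at any sample size. Item 3 offers 8 as sufficient for effectiveness without a derivation, subject to the technical reading allowed above. The second part of the hypothesis has nothing in the plan to test it.

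The attribution gap cannot be sized from the documents; the 0 to 30 points is conditional on the assumed 80%. The conclusion about attribution does not depend on that number. It rests on no comparator for adherence being described in the available text, and on the unseen surveys being what the protocol says they are.

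**What to change.** 1. **Statistical Considerations, items 2 and 3.** Replace the effectiveness wording with: *estimate adherence during MedRem use and describe acceptance and usability*. Align the clinical-value sentence in item 2 and its counterpart in the Background.
2. **Item 3.** Justify 8 completers (10 enrolled) as a feasibility or pre-pilot number.
3. **Objectives/Hypothesis.** Keep the part about patients using the system. Mark the comparison with population averages as not tested in this study, and state that no comparative conclusion will be drawn.

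Alternatively, the sponsor may keep an effectiveness aim by naming a pre-MedRem baseline or a reference value with its source. A baseline would need a measure that does not depend on MedRem prompts, and 8 would then need its own justification (step 5 of the working).

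Optional and secondary: in item 4, report for each patient the confirmed prompts divided by the prompts actually scheduled, separately for medication and exercise. Count unanswered prompts as not confirmed and show the response rate separately. Using prompts actually scheduled allows for the adjustments to reminders and regimens that Study Procedures permits. This clarifies the description but does not supply the missing comparator.

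Cost: the first route changes wording only, leaves patients, procedures and data as they are, and yields a less ambitious stated aim. The alternative costs a baseline period or a defended reference value.
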